6.4.3 Interim Analyses and Data Monitoring

One interim analysis was conducted.

The interim analysis comprised the complete analysis as planned for the final analysis, except for the Health economic modeling analysis, the resource use data, RNA expression and Epitope mapping data, and the PK analyses for patients receiving ITI. All analyses were based on available data at that time.

Time-Point of Analysis

Interim analysis: once 50 patients achieved at least 50 EDs.

For the interim analysis the data to be analysed was frozen in a data snapshot for the analysis.

The final statistical analysis was conducted upon successful completion of all database release (DBR) procedures and sign-off of the DBR release form.

6.4.4 Multicentre Studies

No analysis on between centre effects is planned.

6.4.5 Multiple Comparisons/Multiplicity

Not applicable.

6.4.6 Use of an 'Efficacy Subset' of Subjects

For each efficacy analysis primarily analysed by the intention-to-treat principle, an additional per-protocol set will be defined (See Sections 5.1) for which the most important efficacy analyses will be repeated as a secondary analysis.

6.4.7 Active-Control Studies Intended to Show Equivalence

Not applicable.

6.4.8 Examination of Subgroups

Part of the analyses will be performed in sub-groups defined in Chapter 5.1.

For the combined presentation of subgroup results, Forest plots will be provided.

7 DEMOGRAPHICS AND BASELINE CHARACTERISTICS

The following demographic data will be collected:

- Birth date (Age) or at least month and year, Ethnic origin; “male” will be the standard value for Sex in the CRF.
Age will be calculated from the month and year of birth and the start of the first IMP administration.

Further baseline characteristics are:

- Height, Weight; Body Mass Index (BMI) which will be calculated from height and weight
- FVIII activity (%), FVIII antibody and Bethesda assay result (BU) (both assays) at screening
- Previous and concomitant medications
- Medical history and physical examination
- Underlying F8 gene defect including null/non-null mutation analysis (blood samples collected by the Investigator and analysis performed by a central laboratory)
- Family history of haemophilia and inhibitors against FVIII

All these demographic data and baseline characteristics will be presented in summary and/or frequency tables according to section 6.1 and as listed in section 13.

8 EVALUATION OF TREATMENT COMPLIANCE AND EXPOSURE

Prophylaxis, ITI treatment and treatment of Bes and surgeries: The following will be tabulated and/or summarized:

- Reason for Administration
- Number of Injections
- First dose, last dose, number of Exposure Days
- Total Dose (IU)
- Dose (IU FVIII/kg BW)

Furthermore, the *Human-cl rhFVIII* batches used will be listed for both assays with their potencies in the listings for doses.

9 **EVALUATION OF TREATMENT EFFICACY**

9.1 **Immunogenicity**

All recorded determinations of inhibitors against FVIII will be listed. The absolute number and cumulative incidence of inhibitors (inhibitor titre ≥ 0.6 , < 5 BU and ≥ 5 BU respectively) will be presented in total, and as percentage of the analysis population, with a 95% confidence interval. If justified by the number of events, the time period until the first inhibitor activity will be tabulated and displayed graphically by means of a Kaplan-Meier plot of percentages without inhibitor versus cumulative EDs until appearance of inhibitor, and a logistic regression analysis of incidence rates of FVIII inhibitor development will be performed (prognostic factors: family history of inhibitor, family history of hemophilia, weight, mean dose/ED, age, F8 gene mutation defect (including null/non-null, high/low risk mutation analysis), number of EDs before inhibitor development, age at first treatment, intensity of treatment (number of peak treatment moments), country ethnicity, center).

In addition, number of EDs until inhibitor development will be shown in life-table lists showing the incidence of inhibitors per interval of 5 EDs; a Cox regression will analyse the ED to inhibitor data for the impact of possible prognostic variables (same list as for logistic regression analysis above).

The incidence of low and high titre FVIII inhibitors will also be presented grouped by ethnicity and F8 gene mutations categorized as null/non-null and as high/low risk, incl. results of the immunogenotyping sub-study. For the combined presentation of subgroup results, Forest plots will be provided.

The number of EDs before inhibitor development will be tabulated for each patient with FVIII inhibitors.

RNA expression analysis data and Antitope Ltd. sub-study data will not be analysed under this SAP.

9.2 **Prophylaxis (Prevention of Bleeding episodes)**

The following will be presented following the manners of representation described in section 6:

- Number of subjects treated prophylactically
- Characteristics and number of prophylactic treatments: Treatment intervals, dosage, changes or interruptions in prophylactic treatments
- Number of injections and exposure days. Injections administered over midnight will only count as exposure day on the day on which the injection had started.
- Amount of *Human-cl rhFVIII* used (per month, per year*, exposure day and injection, and in total)

*projected estimate

- Overall efficacy assessment at the end of the study: Number and rate (per month and per year) of spontaneous BEs in subjects on prophylactic treatment*; in total, as well as broken down to intensity of prophylaxis, timely distance from last study drug administration, dose(s) and characteristics of BE (type, site and severity of BE).

*The rate of BEs will exclude BEs and the time period between start of surgery-related prophylactic treatment and re-start of prophylactic treatment after surgery.

It will also exclude BEs and time periods of “on-demand” treatment, if any.

- In two additional secondary analyses, overall efficacy analysis for prophylactic treatment will be analysed
 - for traumatic BEs
 - for all BEs (spontaneous, traumatic, others (if any)).
- Further analysis on bleeding rates will be performed in patients who developed an inhibitor, but only during their inhibitor-free periods. An inhibitor is regarded as confirmed between its start date, as defined in Chapter 3.4.1, Definition “I4”, and the time when the inhibitor titre decreases again to <0.6 BU for the first time, which has to be confirmed by a subsequent measurement of < 0.6 BU; should the inhibitor titre however not have decreased to < 0.6 BU during the study the period with confirmed inhibitor lasts until the end of the study. Periods of prophylaxis without confirmed inhibitor are regarded as “inhibitor-free”.
- Study drug consumption data for prophylactic treatment (IU FVIII /kg BW per month, per year, exposure days) per subject and in total (for subjects on prophylactic treatment) will be presented descriptively.

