- inhibitor level ≥ 0.6 BU at one time point $t_{1,I}$

and retest of sample from same time point $t_{1,I} \geq 0.6$ BU

and inhibitor level ≥ 0.6 BU at a subsequent time point

or

- inhibitor level ≥ 0.6 BU at one time point $t_{1,I}$

and inhibitor level ≥ 0.6 BU at a subsequent time point

and retest of sample from same time point $t_{2,I} \geq 0.6$ BU

or

- inhibitor level ≥ 0.6 BU at three subsequent time points $t_{1,I}, t_{2,I}$ and $t_{3,I}$
(e.g. if retests are not available).

(I3) An inhibitor is confirmed to be a low titre inhibitor, if

- occurrence of inhibitor of < 5 BU is confirmed (according to I2) but

- occurrence of high titre inhibitor (according to I1) is *never* confirmed during the observation period*

(Note: a low titre inhibitor which turns to a confirmed high titre inhibitor according to definition I1 is solely counted as a high titre inhibitor. Inhibitors initially measured as low titre of < 5 BU and remain low titre (< 5 BU) are defined as low titre inhibitors)

*This condition means that a patient only can be defined as having either a low titre inhibitor or a high titre inhibitor. The patient cannot be counted twice.

These definitions for confirmation of positive inhibitors and for high and low titre inhibitors are considered to be relevant for the overwhelming number of inhibitor occurrences. However, there might be cases where additional information (e.g. when taking the whole sequence of inhibitor testing or additional local lab data into account) may suggest that an inhibitor may be assessed rather high titre than low titre. All inhibitor data will be reviewed during the Data Review Meetings before interim analysis/ final analysis to identify such cases.

Time and number of EDs until inhibitor occurrence:

(I4) The time / number of EDs to inhibitor occurrence is defined

- by the time between ED1 and the date of the first positive inhibitor titre detected in a confirmed

inhibitor patient (I2)

- more exactly : as

minimum {date of $t_{1,H}$, date of $t_{1,I}$ } – date of Day 1 (ED1) (days) ,

or the number of EDs (with injections for any indication) during this time frame (ED1 until day before minimum {date of $t_{1,H}$, date of $t_{1,I}$ })

(Note: If different dates for $t_{1,H}$ and $t_{1,I}$ are available, the earlier date will be taken into account)

Censoring: Time / number of EDs until any inhibitor will be censored for patients without inhibitor at date of last available inhibitor testing

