4.4 Study Assessments

For assessments directly related to the evaluation of the primary and secondary endpoints, please refer to section 3.4 (Assessment of Objectives).

The following parameters will be assessed to allow a meaningful characterisation of the study population and to collect background information required for medical evaluation of study events:

- Subject demographics and baseline characteristics:
including ethnicity, age, height, weight, family history of haemophilia and inhibitors against FVIII.
- F8 gene mutation analysis including null/non-null specification
- Immunogenotyping
(HLA-typing, immune response gene profiling, F8 ethnic haplotype determination)
- RNA expression analysis
- FVIII level and recovery determination
- Half-life determination for patients under ITI treatment

- Medical History
- Concomitant Medication will be recorded throughout the trial
- Physical examinations will be performed at screening, at six monthly visits and at the completion visit.

5 **STUDY POPULATIONS**

5.1 **Subject Disposition**

For the analysis of this study the following populations will be considered:

- **Safety analysis population**: All subjects who received at least one dose of *Human-cl rhFVIII*
- **Intent to Treat (ITT) analysis population**: All subjects in the safety analysis population for whom any data was collected post treatment with *Human-cl rhFVIII*

Subpopulations of the ITT population will be

- Subjects of each ethnic group
 - Subjects with ITI treatment
 - Subjects with breakthrough bleedings, if appropriate
 - Subjects with surgical interventions, if appropriate
 - Subpopulations especially for inhibitor incidence analysis:
 - Subjects with different F8 gene mutations
 - Subjects with/without family history of inhibitors
 - Subjects by classes of EDs prior to inhibitor generation (1-5, 6-10, 11-20, 21-50, > 50)
 - Subject's age at first exposure (< 1, 1-6, > 6-12, > 12 months)
 - Subjects by reason for treatment prior to inhibitor generation
 - Subjects by intensity of treatment with/without peak treatment moments before inhibitor appearance (peak treatment moments defined as
 - ≥ 3 subsequent days with FVIII dosing, and/or
 - at least one day with prophylactic doses of > 50 IU FVIII /kg BW)
 - ED50 sub-population: Patients in the ITT population with at least 50 EDs of treatment with *Human-cl rhFVIII*
 - ED20 sub-population: Patients in the ITT population with at least 20 EDs of treatment with *Human-cl rhFVIII*.

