- **Efficacy: Per Protocol (PP) analysis population**: All subjects in the ITT analysis population who completed the trial without significantly violating the inclusion/exclusion criteria or other aspects of the protocol considered to potentially affect the efficacy results.
Especially the following subjects will be excluded from this population:
 - Subjects who violate the following inclusion criteria:
 - severe haemophilia A (FVIII:C < 1%; historical value as documented in subject records),
 - no previous treatment with FVIII concentrate or other blood products containing FVIII
 - Subjects who fulfil at least one of the following exclusion criteria:
 - other coagulation disorder than haemophilia A
 - severe liver or kidney disease (ALT and AST levels >5 times of upper limit of normal, creatinine >120 $\mu\text{mol/L}$),
 - concomitant treatment with any systemic immunosuppressive drug,
 - Subjects who use concomitant medication that may confound study results, like e.g. alpha-interferon or prednisone
 - Subjects with significant non-compliances with the protocol like for example non-compliance to complete the diary in a proper manner or more than 30% of haemostatic efficacy assessments missing.

- Subjects with dosing or treatment errors like e.g. the use of other FVIII products (except for emergencies) or several *unexplained* and significant deviations from the recommended dose regimen.
- Subjects for whom less than a minimum of inhibitor tests is available*
- Patients with less than 95 days of exposure to *Human-cl rhFVIII*.

*Defined during Data Review Meeting for the interim analysis on April 7, 2016:

if less than 1 inhibitor test is available for any of the following periods:

- baseline, if first result of inhibitor screening after first exposure to the study drug is positive (it cannot be assured that the patient is a PUP),
- between ED2 and ED20,
- between ED21 and ED50.

- Population of subjects on prophylactic treatment schedule (PROPH): All subjects in the ITT population who have at least one prophylactic treatment. Only data under prophylaxis will be used for the analyses.
- Per-protocol population of subjects on prophylactic treatment schedules (PROPH-PP): All subjects in the PP population who have at least 95 EDs of treatment and who have no significant dosing or treatment errors, like e.g. unexplained interruptions of the prophylaxis with *Human-cl rhFVIII*.

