- Non-compliance issues raised by the investigator or sponsor.
Dosing or treatment errors like e.g. the use of other FVIII products (except for emergencies) or significant deviations from the recommended dose regimen.
- Less than a minimum of inhibitor tests (see Chapter 5.1, definition of PP population) available
- Less than 100 days of exposure to *Human-cl rhFVIII* at completion (< 95 EDs is regarded as major, 95-99 EDs is regarded as minor protocol deviation; if an inhibitor is detected prior to 95 EDs and the patient switched to ITI treatment, this is not regarded as a protocol deviation)

A list of major protocol violations will also be included in the Clinical Study Report.

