14.2.2.4	T	Statistics on the number of EDs before first confirmed inhibitor activity in patients with low titre inhibitors by intensity of treatment	ITT, PP
14.2.2.5	T	Statistics on the number of EDs before first inhibitor activity in patients with any inhibitors – by reason of treatment (on-demand, prophylaxis, combinations)	ITT, PP
14.2.2.6	T	Statistics on the number of EDs before first inhibitor activity in patients with only high titre inhibitors (on-demand, prophylaxis, combinations)	ITT, PP
14.2.2.7	T	Statistics on the number of EDs before first inhibitor activity in patients with only low titre inhibitors- by reason of treatment (on-demand, prophylaxis, combinations)	ITT, PP
14.2.3.1-3	F	Kaplan-Meier curves on number of EDs until first inhibitor activity (any inhibitor, high titre inhibitor, low titre inhibitor,)	ITT, PP
14.2.3.4-6	T	Kaplan-Meier curves on number of EDs until first confirmed inhibitor activity – Display of product limit estimates (any inhibitor, low titre inhibitor, high titre inhibitor)	ITT, PP
14.2.4.1-3	F	Kaplan-Meier curves on number of EDs until first inhibitor activity by F8 mutation type, null and non-null mutation (any inhibitor, high titre inhibitor, low titer inhibitor)	ITT, PP
14.2.4.4-6	T	Kaplan-Meier curves on number of EDs until first inhibitor activity by F8 mutation type, null and non-null mutation (any inhibitor, high titre inhibitor, low titer inhibitor) – Display of product limit estimates	ITT, PP
14.2.4.7-9	T	Life-tables : Risk of inhibitor incidence over time in steps of 5 EDs (any inhibitor, high titre inhibitor, low titer inhibitor) – Display of life-table estimates	ITT, PP
14.2.5	T	Logistic regression analysis for any, low- and high-titre inhibitors (prognostic factors: family history of hemophilia, family history of inhibitors, weight, mean dose/ED, age, F8 gene mutation defect, null/non-null mutation, number of EDs before inhibitor development, age at first treatment, intensity of treatment, country, center, ethnicity)	ITT, PP
14.2.6	T	Cox regression analysis for any, low- and high-titre inhibitors (initial model with same prognostic variables like in 14.2.5)	ITT, PP
14.2.7	T	Statistics on the number of exposure days and injections administered for ITI treatment with Human-cl rhFVIII	ITI
14.2.8	T	Statistics on the amount of Human-cl rhFVIII (IU) for ITI treatment per month, per year, per exposure day, per injection and in total	ITI

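### The inhibitor regressions list the number of exposure days before inhibitor development as a predictor, although it is the outcome time itself; the peak-treatment count has unequal counting time

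*SAP*

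**What the plan says.** **The models.** The factor list for the logistic regression in SAP 9.1 contains "number of EDs before inhibitor development, age at first treatment, intensity of treatment (number of peak treatment moments", along with mean dose per ED, baseline factors, country and centre. A Cox regression of EDs to inhibitor then uses the "same list as for logistic regression analysis above". SAP 13 repeats this: Table 14.2.5 names the ED term, and Table 14.2.6 is the "initial model with same prognostic variables like in 14.2.5". Protocol 9.2.2 has the same term in its logistic model and plans no Cox model.

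**The variable.** Definition I4 in SAP 3.4.1 sets the time to inhibitor as days from ED1 to the first positive titre, "or the number of EDs (with injections for any indication) during this time frame". Patients without an inhibitor are censored at their last inhibitor test. SAP 9.1 adds: "The number of EDs before inhibitor development will be tabulated for each patient with FVIII inhibitors".

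**Intensity and dose.** SAP 5.1 defines a subgroup: "Subjects by intensity of treatment with/without peak treatment moments before inhibitor appearance". Protocol 9.2.1 uses the same window. SAP 5.1 counts a peak by either of two criteria: at least three dosing days in a row, or a day with a prophylactic dose above 50 IU/kg. SAP 9.1 does not carry the window into the regression count, and no section gives a counting period for patients without an inhibitor. Mean dose per ED has no window anywhere.

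**Status.** SAP 6.4 calls all these analyses exploratory. The logistic model is run only if the number of events justifies it.

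**The concern.** A prognostic factor should be known before the outcome, or at least measured independently of it. The number of EDs before inhibitor development is neither: in the Cox model it is the time axis, and in the logistic model only patients with the event have a value. A model containing it yields no usable estimate for that term and, when factors are fitted together, damages the estimates for mutation type, family history and the rest.

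The peak count raises a milder form of the same problem. Patients who develop an inhibitor leave the counting period early, so they collect fewer peaks whatever the truth. Treatment intensity is modifiable, so a falsely protective result could be read as clinical information. Immunogenicity is the primary objective, and these are the plan's only regression models of inhibitor risk factors.

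**Working it through.** The plan gives no figure to reproduce here. Steps 1 and 2 are algebra; the later steps use simulation or arithmetic with stated assumptions.

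**1. Cox model, ED term alone.** Let T be EDs to inhibitor or to last test, and let the covariate equal T. For a failing patient i with risk set R(i), the log partial likelihood contribution is

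−ln Σ over j in R(i) of exp(β(T_j − T_i)).

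Every T_j − T_i is zero or positive. As β falls, each term with T_j > T_i shrinks to 0, and the sum falls to m_i, the number tied at T_i. The total therefore rises towards −Σ ln m_i and has no maximum at a finite β. The same holds if only inhibitor patients, who alone have a value, are kept.

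One simulated trial (100 patients, 30% risk as in protocol 1.1, assumed exponential onset with mean 15 EDs, 26 events):

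| β | 0 | −0.1 | −0.5 | −1 | −5 | −20 |
|---|---|---|---|---|---|---|
| log partial likelihood | −116.1 | −50.0 | −27.9 | −20.4 | −13.8 | −13.7 |

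In a separate simulation with scheduled testing and median onset at ED 12, the medians were −133.1 at 0, −26.8 at −1, −19.8 at −5 and −19.7 at −20.

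**2. Cox model, joint fit.** At the limit only patients tied at the same ED are compared. Suppose m tied patients all fail and k of them carry a binary baseline factor with coefficient γ. Their contribution is kγ − m ln(k e^γ + m − k), apart from constants. Setting the derivative to zero gives k e^γ + m − k = m e^γ, so γ = 0. Apart from any censored patient tied at the same ED, the factor's hazard ratio is driven to 1 whatever its true effect. In simulation (risk 41% against 16% by a binary factor) it was 2.90 without the ED term and 1.00 at the limit.

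**3. Logistic model.**
- Left missing for inhibitor-free patients: no non-cases remain in the any-inhibitor model.
- EDs to last test substituted: median AUC 0.97 to 0.99, so the variable almost reproduces the outcome.
- A placeholder such as 0: the variable labels the outcome directly.

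**4. Peak count stopped at the inhibitor.** Expected count = peak rate × EDs observed. At an assumed 3 peaks per 100 EDs, an inhibitor patient with 15 EDs expects 0.03 × 15 = 0.45 peaks, and an inhibitor-free patient with 100 EDs expects 0.03 × 100 = 3. With no true effect, at inhibitor rates of 20%, 30% and 44% (400 trials each):

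| Model | Median estimate per peak | p < 0.05 |
|---|---|---|
| Logistic, fixed count | OR 0.16 to 0.20 | 99.8% to 100% |
| Cox, fixed count | HR 0.21 to 0.29 | 100% |
| Cox, time-dependent count | not tabulated | 3.8% to 5.8% |

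Across a wider set of peak rates, patterns and onset times, the fixed count gave OR 0.14 to 0.95 and HR 0.18 to 0.94. If an undetected inhibitor raises the peak rate 3- or 5-fold, the ranges become OR 0.17 to 1.10 and HR 0.21 to 1.08. The documents give no peak rate.

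**5. Mean dose per ED.** Protocol 5.4 gives 20–50 IU/kg for prophylaxis. For immune tolerance induction (ITI) it gives high responders 100–150 IU/kg every 12 hours, that is 200–300 IU/kg per ED, and low responders 50–100 IU/kg. Take 15 EDs at an illustrative 35 IU/kg before the inhibitor:
- cut at the inhibitor: 35 IU/kg;
- 100 high-responder ITI EDs at 200 added: (15 × 35 + 100 × 200) / 115 = 178.5;
- 300 at 300 added: (15 × 35 + 300 × 300) / 315 = 287.4;
- 100 low-responder ITI EDs at 50 added: (15 × 35 + 100 × 50) / 115 = 48.0.

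The unstated window can therefore decide the value.

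**The case against.** The models are exploratory, and a diverging coefficient would be conspicuous in the output. Table 14.2.6 speaks of an initial model, which suggests that terms may be removed later. The logistic term is not useless in every output: Table 14.2.5 also covers low and high titre, and among inhibitor patients high against low titre can still be estimated. On intensity, the plan does state a window, ending at inhibitor appearance. Mean dose per ED is an average, so stopping at the inhibitor does not mechanically lower it.

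Much of this stands, and it limits the point. It does not rescue the ED term: no reduction rule is stated, joint results would be unreliable while the term is in, and high against low titre among cases is a different question from who develops an inhibitor. The stated peak window keeps ITI dosing out of the count but leaves counting time unequal. For mean dose, only the missing window is shown, not a bias under a pre-inhibitor window.

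**Conclusion.** The ED term is an error in the plan as written. With the variable coded as I4 codes it, or kept for inhibitor patients only, the absence of a finite Cox hazard ratio follows from the algebra and needs no simulation assumption. The logistic AUC of about 0.97 to 0.99 and the size of the peak-count bias (OR from about 0.14 to near 1) do depend on assumed onset times, peak rates and patterns. The affected outputs are Tables 14.2.5 and 14.2.6 and the intensity rows of Table 14.2.1.1. The primary incidence with its confidence interval, the Kaplan-Meier curves, the life-tables and single-factor models of baseline factors are not affected.

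A reader might infer three stronger claims that the documents do not support.
- *That the peak count takes in ITI dosing, so the inhibitor creates its own peaks.* The only stated window ends at inhibitor appearance, and Listings 16.2.5.3.1 to 16.2.5.4 separate ITI from other exposure.
- *That no intensity result could be interpreted.* The bias is close to nil in some simulated settings.
- *That the per-protocol logistic model is always completely separated.* SAP 5.1 excludes "Patients with less than 95 days of exposure to" the product, while SAP 5.2 says that "if an inhibitor is detected prior to 95 EDs and the patient switched to ITI treatment, this is not regarded as a protocol deviation". SAP 5.1 also allows exclusion without a deviation. Whether patients with early inhibitors belong to that population is unsettled, and comparing cases before ED 95 with patients required to have 95 EDs separates them by construction.

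**What to change.** 1. Delete the number of EDs before inhibitor development from both factor lists in SAP 9.1 and from Tables 14.2.5 and 14.2.6, and record the change from protocol 9.2.2. Keep it as the time axis and as a description of inhibitor patients. Label the ED-class row of Table 14.2.1.1 accordingly. This costs only wording.
2. In the Cox model, enter peak moments (both SAP 5.1 criteria) and mean dose per ED as time-dependent covariates, using only non-ITI exposure before the current ED. Report unlagged and lagged versions together. The lag should be at least as long as the inhibitor-test interval and the same for all patients at a given ED, and the cumulative window must never move backwards. A lag that steps from 4 to 12 EDs after ED 20 breaks the last condition: the window end falls from 20 − 4 = 16 to 21 − 12 = 9. Both versions are needed. With no true effect, the unlagged model gave HR 0.95 to 1.04 when dosing did not change before detection, but 1.03 to 1.67 when an undetected inhibitor raised the peak rate. A lagged model (4 EDs to ED 23, then 12) gave 0.84 to 1.07. That lag also steps back, from 23 − 4 = 19 to 24 − 12 = 12, so the final rule should be checked by simulation. Programming is modest: infusion dates, doses and reasons are collected.
3. Drop the whole-follow-up peak count from the logistic model and from the intensity rows of Table 14.2.1.1. Alternatively, use a fixed early window among patients still inhibitor-free at its end, and state the events lost. A landmark at ED 10 would lose 23–60% of inhibitors by onset, or 18–54% by detection, under the assumed onset curves.
4. Add a note to any interim output that used these terms. SAP 6.4.3 says that the interim followed the final plan, and its listed exceptions do not include these models.
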